2 STATISTICAL ANALYSIS PLAN

Statistical design, method and the analytical procedures

The patient characteristics of both groups will be compared using the chi square test for categorical data, the t-test for normal divided continuous data and non parametric test for not normally divided continuous data.

If the patient characteristics are not significantly different, no correction will be made, otherwise the data will be corrected using multiple variation analysis.

Continuous outcome variables will be analyzed with general linear modelling which a Bonferoni post hoc test and the data will be compared to the preoperative data.

Clinical data (HHS, HOOS and SF-12) will be presented using 95% confidence intervals while comparing the results between the MHP and Stanmore prostheses.

Differences in the various clinical and laboratory outcomes between treatment groups will be presented with their 95% confidence intervals.

b) Sample size

50 patients. 25 in each group.

This item is described in session A.5.2

c) Level of significance and the power of the clinical investigation

Not relevant, since the power is based on literature (session A 5.2).

d) Expected drop-out rates

Not relevant, since the power is based on literature (session A 5.2).

e) Pass/fail criteria to be applied to the results of the clinical investigation

Table 2: Criteria for decision to continue the study.

	Pass
Safety:	Less than 10% device related complications.
Efficacy	Functional improvement and pain reduction measured with the Harris Hip Score and HOOS compared to preoperative score within the same range as the improvements for the Stanmore hip.
Correctly implanted	Based on standard radiographs 
- A leg length increase between -10 and 5 mm.- Laterization of the head between + 5 and -10 mm.- Circumferential cement mantle.- The bone plug is placed 1 to 3 cm below the prosthesis.

	
- Absence of cement leakage below plug.- Absence of radiolucency between prosthesis and cement in all Gruen zones.
--	---

f) Provision for an interim analysis, where applicable

After 20 patients are included (10 MHP and 10 Stanmore), a 6 weeks waiting period will be used after which the surgeon will decide if the prosthesis is safe according to criteria defined above. An independent orthopaedic surgeon will evaluate the X rays of the first 10 patients with the MHP prosthesis.

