g) Criteria for the termination of the clinical investigation on statistical grounds

- A significant decrease in functional improvement in the MHP group compared to the Stanmore group.
- A significant increase in complications and adverse events in the MHP group compared to the Stanmore group.

h) Procedures for reporting any deviation(s) from the original statistical plan

The used statistical technique depends on the deviation of the variables. Therefore, the exact statistical technique will be determined during the evaluation and will be described in the report.

i) Specification of subgroups for analysis

The first 20 patients will be analyzed for adverse events and function to decide whether the study will continue.

j) Procedures for accounting for all data

The data will be monitored for completeness. If data is complete the file will be closed. If corrections to data are made after closure, the reason for change will be noted. If data is missing the cause will be noted on a specific document. After analysis the number of patients in each subgroup at each time interval will be noted in the tables.

k) Treatment of missing, unused or spurious data, including drop-outs and withdrawals

The study will be performed according to the intention to treat principle. If the patient is revised the last measured data will be carried forward. The data will be analyzed using general linear modelling which can account for some missing data.

l) A justification for excluding particular information from the testing of the hypothesis

Not relevant.

m) In case of multi-centre clinical investigations, the minimum and maximum number of subjects to be included for each centre

Not relevant.

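### Do the differing safety events and the undefined "A significant increase in complications and adverse events in the MHP group compared to the Stanmore group" in item (g) leave this trial without a workable safety rule?

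*Combined protocol and SAP*

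**What the plan says.** Safety is described in several places.

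- **Synopsis, main study parameters:** safety is the absence of device-related complications that are serious.
- **SAP (e):** the item is headed "Pass/fail criteria to be applied to the results of the clinical investigation" and its Table 2 is titled "Criteria for decision to continue the study". The safety row passes below 10% device-related complications, with no seriousness limit and no stated denominator.
- **SAP (f):** after 10 MHP and 10 Stanmore patients and a 6-week wait, the surgeon judges the prosthesis against the criteria already listed, which means Table 2. An independent orthopaedic surgeon reads the X-rays of the first 10 MHP patients.
- **SAP (g):** one of the two statistical grounds for termination is "A significant increase in complications and adverse events in the MHP group compared to the Stanmore group".
- **SAP (i):** "The first 20 patients will be analyzed for adverse events and function to decide whether the study will continue".

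On method, item (c) answers the question about level and power with "Not relevant, since the power is based on literature (session A 5.2"), a section that is not in the available text. Item (h) says "the exact statistical technique will be determined during the evaluation and will be described in the report". The opening of the SAP states "The patient characteristics of both groups will be compared using the chi square test for categorical data" and names general linear modelling for continuous outcomes. It adds: "Differences in the various clinical and laboratory outcomes between treatment groups will be presented with their 95% confidence intervals".

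**The concern.** Two things look wrong.

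First, three sections count three different events: serious device-related complications, all device-related complications, and all complications and adverse events. Nothing states which rule prevails if they point in different directions, or whether Table 2 still applies after the first 20 patients. If it lapses, (g) is the only safety criterion in the available text for the last 15 of the 25 MHP patients.

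Second, (g) is headed as a statistical criterion but has no defined statistic. With samples this small, the choice of test moves the boundary by one or two patients. The trial is open, so a test chosen at evaluation could be chosen with events and allocation in view. At stake is whether the same data from a first-in-human implant would stop the trial or let it run on.

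**Working it through.** **Inputs.** 10 per arm at the interim (SAP (f)) and 25 per arm at the end (SAP (b)). The plan states no boundary, level or power for (g), so there is no figure of its own to reproduce. Assumed here: p < 0.05 two-sided, which the 95% intervals suggest; patients with at least one event as the unit; and true event rates chosen for illustration, since the documents give none.

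**Boundary with 0 Stanmore patients affected.** For 4 MHP patients vs 0 at 10 per arm:

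- Fisher: 2 × C(10,4)/C(20,4) = 2 × 210/4845 = 0.087
- Uncorrected chi-square: 20 × (4×10 − 6×0)²/(4×16×10×10) = 32000/6400 = 5.0, p = 0.025
- Yates: 20 × (40 − 10)²/6400 = 2.81, p = 0.094

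For 5 vs 0 at 25 per arm:

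- Fisher: 2 × C(25,5)/C(50,5) = 2 × 53130/2118760 = 0.0502
- Uncorrected chi-square: 50 × 125²/(5×45×25×25) = 5.56, p = 0.018
- Yates: 50 × 100²/140625 = 3.56, p = 0.059

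**Smallest significant MHP count, two-sided (range over the three tests):**

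| Stanmore patients affected | 10 per arm | 25 per arm |
|---|---|---|
| 0 | 4–5 | 4–6 |
| 1 | 6–7 | 6–8 |
| 3 | 8–9 | 9–11 |

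A boundary of 3 arises only with a one-sided uncorrected chi-square test and no Stanmore patient affected. Because (g) counts all adverse events, a zero control count may be unlikely. At an assumed 30% background its probability is 0.7^10 = 2.8% at 10 per arm and 0.7^25 = 0.01% at 25.

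**How often the choice of test matters.** Summing the product of the two binomial probabilities over all outcomes where at least one of the three tests rejects and at least one does not:

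| Assumed rates, MHP vs Stanmore | 10 per arm | 25 per arm |
|---|---|---|
| 30% vs 5% | 13% | 22% |
| 50% vs 30% | 7% | 10% |

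**Does it change the interim decision?** Table 2, read on the MHP arm, fails at 1 of 10, because 10% is not below 10%. If any one of the 4 events in the 4 vs 0 example is device related, Table 2 has failed whichever test (g) uses.

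The two rules also differ greatly in sensitivity. If the true MHP rate of device-related complications is 30%, Table 2 fails with probability 1 − 0.7^10 = 97% at 10 patients. At 30% vs 5%, (g) fires in 9% to 23% of cases, depending on the two-sided test. Fixing the test would not make (g) the effective safeguard at the interim.

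**At 25 per arm.** If Table 2 still applies, 2/25 = 8% passes and 3/25 = 12% fails. It therefore fails before the lowest two-sided boundary of 4 in (g), provided the events are device related.

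**Do the sections contradict each other?** The events are nested: serious device-related complications lie within device-related complications, which lie within all complications and adverse events. The synopsis defines an endpoint, Table 2 is a condition for continuing, and (g) is a trigger for stopping. Item (i) concerns the same 20 patients as (f), and its two topics match Table 2's safety and efficacy rows. Its stated purpose, deciding on continuation, matches the title of Table 2. The natural reading is that (i) restates (e) and (f).

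**The case for a change.** The strongest opposing case is that a criterion placed under statistical grounds ought to name its statistic, and that writing it down costs nothing. Even with a two-sided 5% level taken as given, 4 vs 0 at 10 per arm is significant by one common test and not by another. Under 30% vs 5% at 25 per arm, about one data set in five (22%) would be read differently by the three tests. Item (h) leaves the technique open in a trial where allocation is visible. If Table 2 lapses after patient 20, nothing else in the available text covers the later patients.

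Most of the factual part stands. Item (g) lacks a test, level, sidedness, counting unit and timed later look, and its relation to Table 2 after patient 20 is unstated.

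The inference to a defect is weaker:

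- Item (h) ties the technique to how the variables behave and requires it to be reported. It may be aimed at the distribution of continuous variables rather than at (g).
- The level is deferred to A.5.2, which cannot be checked here.
- The heading of (e) speaks of the results of the investigation, so Table 2 may well outlast the interim.
- A pooled denominator for Table 2 (1 of 20 passes, 1 of 10 fails) is strained, because (f) asks about the safety of the investigational prosthesis.

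**Conclusion.** No change to the plan follows. The omission is real, but it is missing detail rather than a wrong method. An analyst would ordinarily count patients with at least one event and compare the arms two-sided at 5% with a small-sample test, in line with the planned 95% intervals, and (h) requires the technique to be reported.

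The remaining latitude is one or two patients at the boundary when 0 or 1 Stanmore patient is affected. The tests disagree on 7% to 13% of data sets at 10 per arm and 10% to 22% at 25 per arm. These figures rest on the assumed 5% level, the patient-level count and the two assumed pairs of rates. The latitude matters mainly after patient 20, or when none of the MHP events is device related, because Table 2 governs the interim and is much the stricter rule for device-related events.

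The differing event definitions are a fair trade-off. They are nested, serve different functions and do not strictly contradict each other. Imposing one definition would be a debatable preference and could narrow a deliberately broad trigger for a device not previously implanted in humans. Specifying (g) further would record choices that remain the sponsor's, without supplying a demonstrably better rule. Confidence is limited on whatever A.5.2 may already settle, in particular the level.

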In order to conserve as much bone as possible it has been chosen to use a high subcapital resection. The stem has a rather short length and the entire length remains inside the metaphyseal trabecular bone to ensure a good interdigitation at the cement-bone interface. The short length will increase the interface stresses, both shear stresses in axial loading and normal stresses due to a bending load. Therefore it is chosen to make a shallow neck resection and to add a collar to the stem which rests on the resection surface. This will increase the load transfer to the femur very proximally and will diminish the interface stresses. Proximal load transfer has the additional advantage to protect against stress shielding induced osteopaenia.

The diminished stem-cement surface and the increased stresses at the stem-cement interface are counteracted by longitudinal grooves on the anterior and posterior surface of the MHP stem. Extensive

laboratory testing has shown that the stem-cement interface is able to withstand extreme high loads on the hip joint. The whole MHP reconstruction in laboratory testing showed to have superior strength compared to the natural femur. This protocol aims at the first in vivo implantation.

Objective:**1.1.1.1 Primary objective:**

- To analyze the stability of the MHP using Roentgen stereophotogrammetric analysis (RSA) to predict the long term survival.

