1.1.1.2 Secondary objective

- To analyze the short term (1 year) safety of the MHP compared to the Stanmore hip replacement.
- To analyze the short term (1 year) efficacy of the MHP compared to the Stanmore hip replacement.
- To analyze the long term (10 years) safety of the MHP compared to the Stanmore hip replacement.
- To analyze the long term (10 years) efficacy of the MHP compared to the Stanmore hip replacement using patient based questionnaires.

Study design: Single-centre prospective study with 25 patients in the study and 25 in the control group. Open, RCT (Randomized Controlled Trial) in which the MHP is compared with the standard Stanmore hip prosthesis.

Study population: Patients with osteoarthritis of the hip with no severe co morbidities.

Main study parameters/endpoints:

- Stability measured with RSA at discharge, 3, 6, 12 and 24 months postoperative.
- Safety defined as absence of serious device related complications.
- Efficacy defined as functional outcome measured with HHS and the HOOS preoperatively, 6 weeks, 3, 6 and 12 months and subsequently annually at 2-7 years and at 10 years postoperatively.
- Bone density measured using DEXA preoperative and 6 weeks, 1, 2 years postoperative.
- Quality of life measured with the SF12 preoperatively, 6 weeks, 3, 6 and 12 months and subsequently annually at 2-7 years and at 10 years postoperatively.

Nature and extent of the burden and risks associated with participation, group relatedness:

The MHP has not been implanted in human before. Therefore risks of the MHP in vivo are unknown. Nevertheless, preclinical tests of the MHP showed promising results.

All potential risks for a hip prosthesis are reported in section A4.4.

For the study additional traditional and RSA X-rays need to be made, as well as additional DEXA scans. Therefore the radiology exposure will increase with 6 mSv for the total study (10 years). The average annual natural dose is 2 mSv.

The questionnaires will take approximately 10 minutes at each control visit. The RSA and DEXA scans will take approximately 15 minutes each.

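### The SAP leaves the exact technique to be settled during evaluation, and the synopsis and SAP as supplied fix no RSA motion, visit or contrast and no primary functional score, so results can be selected after data are seen.

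*Combined protocol and SAP*

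**What the plan says.** **Technique.** The opening text of SAP section 2 states: "Continuous outcome variables will be analyzed with general linear modelling which a Bonferoni post hoc test and the data will be compared to the preoperative" values. It also promises 95% confidence intervals for group differences, and item (k) names general linear modelling again. Whether covariates enter depends on the observed data: "If the patient characteristics are not significantly different, no correction will be made, otherwise the data will be corrected using multiple variation analysis".

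Item (h) should describe how departures from the plan are reported. It says instead: "The used statistical technique depends on the deviation of the variables", and therefore "the exact statistical technique will be determined during the evaluation and will be described in the report".

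**Primary endpoint.** The primary objective in the synopsis reads: "To analyze the stability of the MHP using Roentgen stereophotogrammetric analysis (RSA) to predict the long term survival". The endpoint list gives: "Stability measured with RSA at discharge, 3, 6, 12 and 24 months postoperative". Neither names a translation or rotation, a summary measure, a decisive visit, a between-group contrast or a threshold. The pass criteria in Table 2 contain no RSA item.

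**Function.** HHS and HOOS are collected at 11 postoperative visits, and SF-12 on the same schedule. No score or visit is named as primary.

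**Design.** The synopsis describes an "Open, RCT (Randomized Controlled Trial) in which the MHP is compared with the standard Stanmore hip prosthesis", with 25 patients per group. Items (b) to (d) refer sample size and power to section A.5.2, which is not in the supplied text.

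**The concern.** Item (h) is a stated rule, not an omission. It makes the technique depend on how the variables look, and gives no normality criterion, decision rule, masked data review or date on which the plan is locked. With no fixed technique there is also nothing against which a deviation could be recognised.

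The model named earlier does not close this gap. Its terms, contrast and Bonferroni family are undefined, and item (h) reopens it. Comparison with preoperative values cannot be applied to the primary endpoint, because the RSA schedule starts at discharge.

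Followed as written, the plan lets the test, and on the supplied text the RSA motion and visit, be chosen once results are visible. Nominal 5% tests and 95% intervals then lose their stated meaning. The selection can work in either direction. For a first-in-human device the welcome answer on function is no worse than the comparator, and a less sensitive method makes that answer easier to obtain. Item (g) also ties termination to a significant functional deficit without saying which score, visit or test decides it.

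**Working it through.** **The plan's own figure.** The stated size is 25 per arm. It cannot be reproduced, because the supplied text gives no alpha, power, effect or SD. For scale, at an assumed two-sided 5% and 80% power, the detectable difference is (1.960 + 0.842) × √(2/25) = 0.79 SD. A 0.8 SD difference is therefore used below.

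**Inputs from the documents.** 25 per arm. RSA at discharge, 3, 6, 12 and 24 months. Functional visits: 4 in the first year, 6 at years 2 to 7, and 1 at year 10, which makes 11.

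**Assumptions.** Two-sided 5%. Discharge is the RSA reference, leaving 4 follow-ups. Six motions (3 translations, 3 rotations). Correlations as shown. Normal data.

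**Step 1: open motion and visit.** With independent tests the chance of at least one false difference is 1 − 0.95^k: 18.5% for k = 4, 26.5% for k = 6 and 70.8% for k = 24. With correlation it was simulated (20,000 null trials). Each motion and visit was compared by t = (difference in means)/√((s₁² + s₂²)/25) on 48 df, counting any p below the threshold.

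| Correlation between motions | Correlation between visits | Any of 24, p < 0.05 | Bonferroni over 4 visits, p < 0.0125, motion free | One motion and visit fixed |
|---|---|---|---|---|
| 0 | 0.5 | 64.1% | 23.3% | 5.0% |
| 0.3 | 0.5 | 60.3% | 22.0% | 5.0% |
| 0 | 0.8 | 51.5% | 17.6% | 4.8% |
| 0.3 | 0.8 | 48.3% | 16.9% | 5.1% |
| 0.5 | 0.9 | 35.3% | 11.9% | 4.8% |

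Repeat simulation moved the ends of these ranges by a point or two (37% to 63%, and 13% to 24%). Bonferroni over all 24 gives 1 − (1 − 0.05/24)^24 = 4.9% if the tests are independent, and less if they are positively correlated.

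**Step 2: open technique.** One outcome at one visit, with no true difference and correlation 0.5 with baseline. A false positive is counted if any method on the list gives p < 0.05:
- t-test or rank test on change: about 6%
- ANCOVA or rank test on change: about 7.6%
- t-test, rank test or ANCOVA: about 8%
- five methods (t-test on score, t-test on change, ANCOVA, rank test on score, rank test on change): about 11%

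These are ceilings for each list, because they assume that the most favourable method is always the one reported.

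**Step 3: hiding a deficit.** With a true 0.8 SD difference and the same five methods, ANCOVA gives p < 0.05 in about 88% of trials, but all five do so in only about 61%. In the remaining 39% (100 − 61), at least one ordinary method would show no significant difference.

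**Step 4: function.** For HHS and one HOOS score over 11 visits (22 tests, correlations 0.5 to 0.7), the chance of at least one false difference is 36% to 49% uncorrected, and 5% to 8% with Bonferroni over visits.

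**The case against.** The SAP does name a method. It specifies a model family and a Bonferroni post hoc test, refers to preoperative values, and promises confidence intervals for group differences. Item (h) most naturally means that the choice follows the distribution of the variables; it does not invite choice by result. The t-test and non-parametric tests in the SAP are for patient characteristics, so the five-method menu above is an assumption of this review. All of this stands. It is why 6% to 8% is the fairer figure for the open technique and 11% an outer case.

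Bonferroni also matters. Applied to all 24 RSA tests it would remove the inflation. The SAP does not define the family, so the uncorrected range cannot be taken as what the plan prescribes, and control cannot be taken as assured.

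Four stronger readings are tempting, and the documents do not support them:
- A reader might infer that the analysts or RSA readers will know the arms. "Open" describes the trial; the documents describe no masking of readers or analysts, but do not say that they are unmasked.
- A reader might infer that no RSA variable is defined anywhere in the protocol. Section A.5.2 is not in the supplied text and could define one.
- A reader might infer that the trial has a false-positive rate above one third. The supplied text sets no between-group test for RSA at all: the primary objective is worded for the MHP alone, and only the secondary objectives are stated against the Stanmore.
- A reader might infer that selection is intended. The text shows only that it is possible.

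**Conclusion.** The concern holds with these limits. Item (h) leaves the exact technique open until evaluation, and the named model is too incomplete to constrain it. The larger gap is the undefined RSA endpoint: free choice of motion and visit costs far more (about 35% to 64% uncorrected, 12% to 23% with Bonferroni over visits only) than free choice of test (about 6% to 8%). With one motion, visit and model fixed, the rate returns to about 5%. The percentages depend on the assumed motions, correlations and alpha, so they show scale and do not predict this trial's error rate. If section A.5.2 names an RSA motion and visit, the RSA part shrinks accordingly, but item (h) would still leave the technique open. The sponsor should correct this.

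**What to change.** 1. Replace the text of item (h) so that it only records and justifies departures from a fixed plan.
2. Before any comparative data are analysed, fix one primary RSA motion, one visit and one MHP-minus-Stanmore contrast with a 95% confidence interval. Use the one in section A.5.2 if it names one. Otherwise choose one, for example stem subsidence from discharge to 24 months; the supplied text does not name this variable, so it is only an example. Label other motions and visits secondary.
3. For HHS, HOOS and SF-12, fix one model with treatment, visit, treatment by visit and preoperative score. This replaces adjustment triggered by baseline significance tests.
4. Name one primary functional score and visit, for example HHS at 12 months, which matches the 1-year efficacy objective. Without this, the model in point 3 still yields 11 visit contrasts per score.
5. If residuals are skewed, report a log-scale or rank analysis as a labelled sensitivity analysis, never as a replacement.
6. Define the family to which Bonferroni applies, and state whether the RSA reader and the analyst are masked to arm.

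The cost is SAP wording: no added patients, visits or scans. The downside is less freedom to adapt the method after seeing the data, which the sensitivity analysis largely covers.

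### Section k carries the last value forward after revision and exempts no outcome, so a stem revised for loosening can enter the RSA analysis with too little migration

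*Combined protocol and SAP*

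**What the plan says.** Section k of the SAP, on missing data and drop-outs, makes three statements. The first sets the framework: "The study will be performed according to the intention to treat principle". The next is the rule at issue here, and it covers revised patients: "If the patient is revised the last measured data will be carried forward". The last one turns to gaps in the data and relies on the model: "The data will be analyzed using general linear modelling which can account for some missing data".

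None of them names an outcome or excludes one. Section l, on excluding information from hypothesis testing, is answered as not relevant. Section h leaves the choice of technique until the evaluation, but it does not withdraw the carry-forward rule.

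The primary objective in the synopsis is stem stability by RSA, as a predictor of long-term survival. The main endpoints list gives the schedules: "Stability measured with RSA at discharge, 3, 6, 12 and 24 months postoperative" and "Bone density measured using DEXA preoperative and 6 weeks, 1, 2 years postoperative". HHS, HOOS and SF-12 are collected before surgery, at 6 weeks, at 3, 6 and 12 months, yearly from year 2 to year 7, and at year 10.

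Revisions can also count on the safety side. Table 2 requires "Less than 10% device related complications", and section g lists as a ground for termination "A significant increase in complications and adverse events in the MHP group compared to the Stanmore group".

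**The concern.** RSA is used here because early migration is taken to foretell loosening. A stem revised for loosening within two years is therefore the case the RSA comparison should reflect most clearly. Carry-forward fixes that stem at its last examination before revision. If it was still migrating, its later values are too low and the arm looks more stable than it was. In the extreme case, revision before the month 3 examination, the only earlier scheduled value is the one at discharge. If discharge is the reference, that value is zero migration, so the failed stem enters as the most stable one.

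The rule also conflicts with the text around it. A carried-forward value is not missing as far as the model is concerned, so the sentence about modelling missing data cannot help revised patients. Patients can still complete HHS, HOOS and SF-12 after revision. Replacing those answers with an old score conflicts with the intention-to-treat principle stated in the same section.

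**Working it through.** The plan gives no figure on this point to reproduce. The arm size of 25 comes from section b. All migration values below are assumptions for illustration.

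**Inputs.** n = 25 stems per arm. RSA at discharge, 3, 6, 12 and 24 months (synopsis). Assumed: unrevised stems average 0.5 mm at 24 months; a failing stem left in place would have reached f = 1 to 5 mm; SD 0.3 mm; discharge is the reference. Let k be the number of revised stems and p the share of f reached at the last RSA before revision.

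**Formulas for the 24-month arm mean**

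- Had migration continued: ((25 − k) × 0.5 + k × f) / 25
- Carry-forward: ((25 − k) × 0.5 + k × f × p) / 25
- Revised stem left out: 0.50

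**Revision before month 3 (p = 0)**

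- One stem, carry-forward: 24 × 0.5 / 25 = 0.48 mm. Continued: (12 + 1) / 25 = 0.52 to (12 + 5) / 25 = 0.68 mm.
- Two stems, carry-forward: 23 × 0.5 / 25 = 0.46 mm. Continued: (11.5 + 2) / 25 = 0.54 to (11.5 + 10) / 25 = 0.86 mm.
- The fall below 0.50 for one stem is 0.02 mm. The standard error is 0.3 / √25 = 0.06 mm, so this is a third of a standard error.

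If discharge is not the reference and the stem has no migration value, it drops out and the mean is 0.50. An unscheduled RSA before revision would change the carried value.

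**Later revision of one stem**, carry-forward mean over f = 1 to 5 mm (continued: 0.52 to 0.68)

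| Last RSA | Linear migration (p) | Mostly early migration (p) |
|---|---|---|
| 3 months | 0.485–0.505 (0.125) | 0.504–0.60 (0.60) |
| 6 months | 0.49–0.53 (0.25) | 0.51–0.63 (0.75) |
| 12 months | 0.50–0.58 (0.50) | 0.516–0.66 (0.90) |

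The arm mean falls below 0.50 only when f × p is under 0.5. With linear migration this means f under 4 mm (last RSA at 3 months) or under 2 mm (6 months), and it does not happen in this range at 12 months. With mostly early migration it never happens.

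**Rank version, revision before month 3.** Suppose unrevised stems are alike in both arms and all migrate more than 0. The chance that a random MHP stem migrates more than a random Stanmore stem, with one MHP stem revised, is:

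- Carry-forward: (24 / 25) × 0.5 = 0.48
- Left out: 0.50
- Worst rank: 0.48 + 1 / 25 = 0.52

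No failure size is needed. With two stems the figures are 0.46, 0.50 and 0.54. The null standard error at 25 per arm is √(51 / (12 × 25 × 25)) ≈ 0.08, so 0.48 against 0.52 is about half a standard error.

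**Scores.** Visits after surgery: 4 in the first year, 6 in years 2 to 7, and 1 at year 10, so 11. Revision before 6 weeks would let the preoperative score fill all of them.

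**Check of the proposed model.** A small simulation used 60 arms per case, SD 0.3, error SD 0.1, failing stems heading for 3 mm, visit as a category, and a random intercept and slope. Over 14 cases (one or two stems; revision before month 3, or last RSA at 3, 6 or 12 months under each migration pattern), the mixed model came closer than carry-forward to the mean without revision in 12, tied in one and was worse in one. Before month 3 it recovers almost nothing: with one stem, 0.50 against 0.48 from carry-forward, where the mean without revision is 0.60. Its worst case was two stems, last RSA at 12 months and mostly early migration: 0.75 against 0.71, an overshoot of 0.04 mm (carry-forward gave 0.69). Convergence warnings arose in 0 to 33 of the 60 fits, so these figures are rough.

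**The case against.** The best defence is that the rule was never meant for RSA. The SAP does not mention RSA. Its sentence on continuous outcomes sets results against preoperative values, which suits the scores and DEXA but cannot suit RSA, whose first examination is at discharge. The document also refers to sections outside the available text, where RSA handling and the reference examination may be set out. This makes the application to RSA less certain, but it exempts nothing. If only the scores were meant, the available text has no rule for a revised stem in the RSA comparison, and a sentence is still needed.

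A second defence is that safety reporting picks up the revision. It can, but that does not correct the RSA comparison. A third is that the effect is small. That stands for the arm mean. A stable stem revised for infection would also be little affected.

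Two stronger readings are tempting and should not be drawn. A reader might infer that a revised stem disappears from the RSA result, or that the rule usually reverses it. The later-revision table shows otherwise: in most of those cases the stem still raises the arm mean, only by less than it should. A reader might also take the registry survival of about 95% at ten years (25 × 0.05 = 1.25 stems) to mean that one early loosening should be expected. That figure covers revision for any reason over ten years, and the Rationale says that mechanical causes have become less common, with infection and malpositioning now leading. The synopsis calls the in vivo risks of the MHP unknown. One early revision is a what-if, not a forecast.

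**Conclusion.** The point holds, with limited size. As written, section k applies carry-forward to every outcome, including the primary one. For RSA it weakens the signal from a stem revised for loosening while still migrating. It moves the arm result the wrong way mainly when revision precedes month 3 and discharge is the reference. In the what-if of one stem in 25, that is 0.48 mm against 0.50 if left out, and a rank probability of 0.48 against 0.50 if left out and 0.52 with worst rank. With later revision the effect is mostly attenuation, and it is small if most migration is early.

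For the scores, the conflict with intention to treat is plain from the text, but the direction of bias cannot be stated. Confidence is medium, because section k does not name RSA and the reference examination is not given in the available text. The rule should be replaced because it can bias the primary comparison and is cheap to change, not because a large distortion is likely.

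**What to change.** Delete the carry-forward sentence from section k and replace it by outcome.

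- **RSA and DEXA:** analyse observed values up to revision in a repeated-measures mixed model, which keeps incomplete series. State the RSA reference examination, or point to the section that does. Report revisions by arm and reason beside the RSA result.
- **RSA sensitivity analysis:** the mixed model recovers almost nothing for revision before month 3, so pre-specify one rank-based 24-month analysis that gives revised stems the worst rank. Report it for all causes, and limited to loosening or instability where the recorded reason allows. The all-cause version matters because in an open trial the reason is recorded with knowledge of the implant.
- **HHS, HOOS and SF-12:** analyse all scores observed at scheduled visits by randomised arm. Say whether those visits continue after revision, if no other section does.

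The cost is SAP wording, one sensitivity analysis in two versions and one table; no extra patients are needed. The downsides are a little more analysis, a possibly less favourable MHP result, and a mixed model that can overshoot slightly (up to about 0.04 mm in the illustration) when revision is late and migration mostly early.
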